Statistical analysis plan – A controlled trial investigating the effects of mindfulness

Inclusion criteria: All pregnant women who had registered at one of the 63 antenatal clinics in Stockholm County between 2016-11-01 and 2018-01-31 were eligible for the study.

Exclusion criteria: Multiple pregnancies.

Causal factors: The 63 antenatal clinics were randomized to two groups, one designated as the Mindfulness group, the other as the Standard-care group. Midwives at the clinics in the Mindfulness group employed the Mindfulness method; midwives at the Standard-care clinics continued to employ established methods.

All the women registered at an antenatal clinic practicing standard care belong to the Standard-care group, and all women registered at a clinic practicing Mindfulness belong to the Mindfulness group.

Observation time, primary outcome measures: The women are monitored from gestational week 32+0 onward until the delivery. The primary outcome measure is determined by the baby's Apgar score measured five minutes after birth. The adverse outcome category is defined as an Apgar score under seven. A stillbirth is scored as 0 and thereby included in the adverse outcome category.

Observation time, secondary measures: The women are monitored from gestational week 32+0 onward until the delivery, the secondary outcome measure is determined by the number of times the woman seeks help at an obstetric clinic because of concern with decreased or altered fetal movement

Observation time, tertiary outcome measures: The woman is monitored from gestational week 32+0 onward until the delivery. The tertiary outcome measure is determined by the baby's Apgar score measured five minutes after delivery. The adverse outcome category is defined by an Apgar score less than four. Stillbirth is recorded as Apgar 0 and thereby included in the adverse outcome category. Another tertiary outcome measure is determined by the baby's death at birth or within seven or respectively 27 days after delivery. Tertiary outcome measures include as well small for gestational age (SGA) and being transferred to the neonatal ward after delivery.

Possible maternal confounding factors: Country of birth, age, body mass index (BMI), previous or current illness educational level, employment, tobacco use, parity, previous intrauterine fetal death, assisted fertilization.

Possible child-related factors: Lethal malformation, lethal illness, genetically related illness.

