Possible mediating confounding factors: C section, induced delivery.

Analysis procedure: The analyses will follow the *intention-to-treat* principle. Complete-case analyses will be done alongside with analyses on imputed data sets. Imputation will be

carried out when the possibility of confounding is analyzed. The method that we will use is “multiple imputation by chained equations method (MICE)”. A total of 50 imputed data sets with imputed values for missing information of the possible confounding factors will be calculated. The basis of the imputation will be possible confounding factors in which information is at hand. A prevalence ratio (percentage ratio, ratio with the percentage of the adverse outcome category in the Mindfetalness group and Standard-care group, respectively) will be used as the metric of association. Log-binomial regression will be used to model the prevalence ratio when adjusting for possible confounding factors. Log-binomial regression will also provide 95 percent confidence intervals. If a log-binomial model does not converge a modified regression model according to Zou will be employed. Logistical regression, modelling odds ratio, will be considered if the model regression model according to Zou does not converge.

Possible mediating factors: Mediating factors will be studied in two ways: partly by dividing into subgroups and partly by introducing a variable that represents a possible mediating factor into a statistical model. When a possible mediating factor is introduced into the model, the change in the modeled adjusted prevalence ratio will be interpreted as a metric of the relative effect of the mediating factor.

More information: More information can be found in two published articles, see below, as well as in <https://clinicaltrials.gov/ct2/show/NCT02865759?term=[name]&rank=1>.

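### The change in the prevalence ratio after adding C-section or induction is to be read as the mediator's effect, but shared causes and stillbirths before labour can make that reading wrong

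*SAP*

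**What the plan says.** The SAP lists two variables: "Possible mediating confounding factors: C section, induced delivery". Under *Possible mediating factors* they are to be studied "partly by dividing into subgroups and partly by introducing a variable that represents a possible mediating factor into a statistical model". For the second of these approaches the reading is fixed in advance: "the change in the modeled adjusted prevalence ratio will be interpreted as a metric of the relative effect of the mediating factor".

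Four other statements bear on this.

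- *Causal factors*: "The 63 antenatal clinics were randomized to two groups". A woman's group follows from the clinic where she registered, so it is set before any induction or C-section.
- *Observation time, primary outcome measures*: "A stillbirth is scored as 0 and thereby included in the adverse outcome category".
- The maternal list begins "Possible maternal confounding factors: Country of birth, age, body mass index (BMI), previous or current illness educational level, employment, tobacco use, parity" and ends with previous fetal death and assisted fertilization.
- The child list is "Possible child-related factors: Lethal malformation, lethal illness, genetically related illness".

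Neither list contains a measure of non-lethal fetal condition in late pregnancy or labour. The SAP states no condition for the reading rule, no sensitivity analysis, no exploratory label, and no rule for births in which the fetus died before labour.

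**The concern.** Randomising clinics protects the comparison of the two groups. It does not protect that comparison once the model also conditions on something that happens after allocation. For the change in PR to measure mediation, two conditions are needed: no uncontrolled cause shared by mediator and outcome, and a mediator that comes before the outcome. Both are doubtful here.

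1. **Shared cause.** Acute fetal compromise is a plausible reason both to intervene and for a low Apgar score. This is general reasoning; the SAP neither states it nor rules it out, and neither list covers it.
2. **Time order.** For a death before labour, the adverse outcome has already occurred when the woman is induced or has a C-section. The delivery cannot mediate it. This route needs no unmeasured cause.

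Subgroups by mode of delivery condition on the same variables and have the same problem. At stake is a report that C-section or induction explains, or does not explain, the trial's result when the data cannot show either.

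The heading *Possible mediating confounding factors* is a separate, smaller matter. The mediation paragraph implies that these variables enter only in a later step, so the heading is a labelling fault and not an error in the main model.

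**Working it through.** The SAP gives no figure to reproduce: no event rate, C-section rate, induction rate or stillbirth share. **Every input below is an assumption.**

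**Method.** Enumerate exactly P(compromise) × P(C-section | arm, compromise) × P(low Apgar | compromise, C-section). Then fit a log-link Poisson model on arm and C-section to the exact cell means. Log-binomial fits agree within 0.001 in the cases shown. Share credited to the mediator = 1 − ln(adjusted PR) / ln(total PR).

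**Inputs for A and B.** 2% of fetuses compromised; low-Apgar risk 0.8% in the others; control-arm C-section 70% in compromised and 16% in other fetuses; risk ratio r, compromised to other, of 2, 3, 5, 10 or 25.

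**A. C-section inert, arm inert (true PR 1.00).** The intervention arm differs only in C-section among the others, 3 points lower or higher.

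| r | adjusted PR, 3 points lower | adjusted PR, 3 points higher |
|---|---|---|
| 2 | 1.002 | 0.998 |
| 3 | 1.005 | 0.996 |
| 5 | 1.009 | 0.993 |
| 10 | 1.019 | 0.985 |
| 25 | 1.040 | 0.968 |

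The mechanism by hand, at r = 5 with C-section 3 points lower (13%):

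- Compromised share of C-section births, control: 0.02×0.70 / (0.02×0.70 + 0.98×0.16) = 0.0140/0.1708 = 8.20%.
- Intervention: 0.0140 / (0.0140 + 0.98×0.13) = 0.0140/0.1414 = 9.90%.
- PR among C-section births: (1 + 4×0.0990) / (1 + 4×0.0820) = 1.396/1.328 = 1.051.
- Among other births the compromised shares are 0.006/0.8292 = 0.724% and 0.006/0.8586 = 0.699%, so the PR is 1.0280/1.0289 = 0.999.

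The subgroup analysis would show 1.051 and 0.999, and the model 1.009, where nothing is mediated and there is no effect.

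**B. The whole effect runs through C-section.** The intervention raises C-section from 70% to 85% in compromised and from 16% to 19% in other fetuses. The adjusted PR should be 1.00 and the credited share 100%.

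Total PR at r = 5 and C-section risk ratio 0.8:

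- Control: 0.98×(1 − 0.2×0.16) + 0.02×5×(1 − 0.2×0.70) = 0.94864 + 0.08600 = 1.03464.
- Intervention: 0.98×(1 − 0.2×0.19) + 0.02×5×(1 − 0.2×0.85) = 0.94276 + 0.08300 = 1.02576.
- Ratio: 0.9914. The fitted adjusted PR is 0.9901, further from 1 instead of at 1.

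| r | RR 0.8: total → adjusted | credited | RR 0.5: total → adjusted | credited |
|---|---|---|---|---|
| 1 | 0.9933 → 1.0000 | 100% | 0.9823 → 1.0000 | 100% |
| 2 | 0.9928 → 0.9974 | 64% | 0.9809 → 0.9971 | 85% |
| 3 | 0.9923 → 0.9948 | 33% | 0.9796 → 0.9943 | 72% |
| 5 | 0.9914 → 0.9901 | −16% | 0.9770 → 0.9889 | 52% |
| 10 | 0.9894 → 0.9794 | −95% | 0.9712 → 0.9767 | 19% |
| 25 | 0.9849 → 0.9558 | −196% | 0.9574 → 0.9480 | −23% |

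With no shared cause (r = 1) the rule is exact. Prevalence of compromise matters: at r = 5 the RR 0.8 case credits 31% at 1% prevalence and −75% at 4%; the RR 0.5 case credits 71% and 28%.

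**C. Stillbirth route (true PR 1.00, induction inert).** Adverse outcome 1.1% in both arms; 10% to 30% of it death before labour; 50% to 90% of those deaths followed by induction, equally in both arms; induction in all other births 18% in control against 15% or 21%.

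- Smallest shifts (10% share, 50% induced): adjusted PR 0.994 and 1.007.
- Largest (30% share, 90% induced): 0.961 and 1.048.
- Zero stillbirth share: exactly 1.000.

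**The case against.** The strongest reply concerns weight, not truth. The primary comparison is untouched. The SAP calls these factors possible mediators and the change only a metric. Comparing the PR with and without a mediator is a recognised approach, and it is exact when there is no shared cause and no stillbirth. Every rate above is assumed. The reversal at r = 5 is a move from 0.9914 to 0.9901, or 0.0013; it looks dramatic only because the credited share divides by a logarithm close to zero. Part of any shared cause may be captured by listed factors such as maternal illness, so the real distortion may be smaller.

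Effects as small as those in B could also hardly be detected. Assuming 1% risk and 10,000 to 40,000 women per arm (not in the SAP), the standard error of ln PR is about √(2/100) = 0.14 to √(2/400) = 0.07 before clustering.

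Much of this stands. The absolute shifts are small, and the percentages must be read beside them. A larger effect can be tested under other assumptions: direct PR 0.80, an inert mediator, 5% compromised at tenfold risk from a 0.7% baseline, mediator 60% against 20%, and allocation changing it by a ratio of 0.8 to 1.25. The adjusted PR then runs from 0.824 to 0.769. The rule would credit the inert mediator with 1 − ln 0.824/ln 0.80 = 13%, or −18% at 0.769. That error is modest, but it is still an error in the very quantity the rule interprets.

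What does not stand is the suggestion that the SAP treats this as exploratory. It prescribes the interpretation without condition. Nor does custom restore time order when the outcome includes deaths before labour.

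**Conclusion.** The concern holds. Followed as written, the rule can credit mediation where there is none, or understate or reverse it where it is complete. This rests on the SAP's unconditional wording, the timing of C-section and induction after allocation, the two adjustment lists, and the inclusion of stillbirth in the outcome. It also rests on the plausible but undocumented premise that fetal condition drives both intervention and low Apgar.

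Under the assumed rates, the spurious shift in PR is mostly 4% or less, at most about 5%, and under 1% through the shared cause at r of 2 to 5. Where C-section carries the whole effect, that effect is itself only about 1% to 4%, so a small shift can be as large as what is being measured. Only the explanatory analysis is affected. The adjusted PR would be at risk only if the heading led someone to place C-section and induction among the confounders.

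**What to change.** 1. Remove the word confounding from the heading, and state that C-section and induction are not in the main adjusted model.
2. Delete the sentence that reads the change in PR as the mediator's effect.
3. Label the mediator-adjusted results and the mode-of-delivery subgroups descriptive and exploratory.
4. Only if mediation is to be claimed: name a method that defines direct and indirect effects, add a sensitivity analysis for mediator-outcome confounding, and state how stillbirths before labour are handled in that analysis.

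Items 1 to 3 cost SAP wording only. An exploratory analysis loses its causal reading; the primary analysis does not change. Item 4 adds analysis work, and only if the claim is wanted.
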